12. STATISTICAL ANALYSIS

- *Describe how your data will be used to test the hypotheses.*
- *State clearly what variables will be tested and what statistical tests will be used.*

- *Include sample size calculations.*
- *If this is a pilot study, state which variables will be examined for hypothesis generation in later studies.*

Blinding:

Due to the nature of the intervention (bolus block, continuous infusion pump), it is not possible to blind the physicians or patients.

Consent:

Consent will be obtained during the preoperative visit, prior to surgery.

Randomization:

Subjects will be randomly assigned in a 1:1 ratio to either bolus block or continuous catheter. The randomization will be stratified by hospital (Plainview, Franklin, Huntington, Long Island Jewish, or North Shore University Hospital).

The Biostatistics Unit will develop a randomization procedure using a permuted block design within the Biostatistics Randomization Management System (BRMS).

Additional details of the procedure, including required record keeping, will be further developed upon approval of this protocol. The Biostatistics Unit has extensive experience in implementing and in producing detailed documentation for such procedures.

Intention to Treat (ITT):

All analyses will be carried out according to the ITT principle. The ITT population will be all subjects randomized, regardless of what treatment they actually received. All patients will be analyzed in the group to which they were randomized.

Statistical Considerations:**Specific Aims:**

To compare the efficacy of two postoperative pain control methods (bolus block, continuous catheter) in patients undergoing ACL reconstruction.

Primary Outcome

Outcomes measured on post-operative days 0, 1,2,3,4,7, and at the post-operative follow-up visit. (Outcomes for days 0, 1,2,3,4, and 7 will be obtained via email and electronic surveys . Outcomes for the post-operative follow-up visit will be measured during the postoperative visit which takes place between days 10 and 14. This will be referred to as "Day 10").

- Pain Control

- Maximum pain will be measured on a scale of 0 to 10, where 0 represents no pain and 10 represents the worst possible pain. Patients will report the maximum pain felt in the 24 hours
- Current pain will be measured on a scale of 0 to 10, where 0 represents no pain and 10 represents the worst possible pain.
- Daily opioid consumption (expressed as morphine equivalents).

Secondary Outcomes

Outcomes measured on post-operative days 1,2,3,4,7, and at the post-operative follow-up visit.

- Quality of Sleep
 - Trouble falling asleep due to pain (yes,no)
 - Wake due to pain (yes,no)

Outcomes measured at post-operative follow-up visit

- Satisfaction with surgery, on a scale of 0 to 10, where 0 represents extremely dissatisfied and 10 extremely satisfied
- Adverse events: Adverse events will be assessed at each visit. At the end of the study, each subject will be categorized as having had one or more adverse events, or not having had any adverse events.
- Serious Adverse events: Serious adverse events will be assessed at each visit and via telephone on post-operative day 1, 2, 3, 4 and 7. At the end of the study each subject will be categorized as having had one or more serious adverse events, or not having had any serious adverse events.

Statistical Methods:

Primary Outcomes:

For each outcome, repeated measures analysis of variance (RMANOVA), where post-operative pain control method (bolus block, continuous catheter) is the between subjects effect and post-operative day is the within subjects effect will be used to examine the association between pain control method and that outcome. Site (stratification variable) will be included as a covariate in each model. The interaction of post-operative control method and day will be included in the model. If the interaction is significant, then pairwise comparisons of pain control method at each day will be carried out within the RMANOVA model. If the usual assumptions required for the ANOVA model are not met, then a suitable transformation, or an appropriate non-parametric method will be used.

Secondary Outcomes:

For binary outcomes measured on days 1,2,3,4,7 and 10:

For each outcome, a generalized linear mixed model (GLMM) for binary clustered (i.e., hierarchical) data will be used to examine the association between pain control method and that outcome. GLMM will be used to account for the hierarchical structure of the data, (namely, multiple days within a subject). Site (stratification variable) will be included as a covariate in each model.

For binary outcomes measured on day 10 only:

For each outcome, logistic regression will be used to examine the association between pain control method and that outcome. Site (stratification variable) will be included as a covariate in each model.

For satisfaction with surgery:

Analysis of variance (ANOVA) will be used to examine the association between pain control method and satisfaction with surgery. Site will be included as a covariate in the model. If the usual assumptions required for the ANOVA model are not met, then a suitable transformation, or an appropriate non-parametric method will be used.

Sample Size Justification:

In a published study of 85 patients undergoing arthroscopic shoulder surgery, patients were randomly assigned to catheter (43 patients) or single-shot block (42 patients) for postoperative analgesia. Median pain with movement on day 3, measured on a visual analog pain scale, 6 in the single-shot group and 4 in the catheter group. As there is limited information available regarding postoperative pain levels following ACL reconstruction, we will assume that the difference in pain levels between bolus block and continuous catheter will be similar (i.e. continuous catheter will be 2 points lower than bolus block). The standard deviation will be estimated as 2.5. This estimate was obtained by dividing the range (10-0) by 4.

The proposed analysis will examine pain levels over multiple days during the postoperative period. If a significant interaction between treatment and day is found, it will be of interest to determine which days differ. Although this comparison will be carried out within the ANOVA model, the 2 sided two sample t-test will be used for purposes of calculating the required sample size. A sample size of 39 subjects per group will yield 80% power to detect a 2 point difference between the two groups on any single day using a two sided two-sample t-test at the 0.01 significance level. The reason for applying this “Bonferroni-type” adjustment is that pairwise comparisons will be carried out for 6 different days, and with this number of statistical tests, it is more likely to find a significant difference at the nominal 5% level when one does not actually exist. Based on our experience, most, if not all patients return for the postoperative visit, and therefore, no adjustment for drop-out has been made. Therefore, the proposed sample size will be 78 subjects (39 for each treatment group). |

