- Significant study intervention non-compliance

- If any clinical adverse event (AE), laboratory abnormality, or other medical condition or situation occurs such that continued participation in the study would not be in the best interest of the participant. Adverse events or unanticipated events will be assessed on a case by case basis and discontinued as noted in the section above.
- If the participant meets an exclusion criterion (either newly developed or not previously recognized) that precludes further study participation.
- An investigator will discontinue/withdraw a patient from study participation if they are not deemed contactable, this will be defined as inability to contact after 3 separate attempts are made at least 2 hours apart across two days.

The reason for participant discontinuation or withdrawal from the study will be recorded on the Case Report Form (CRF) as noted in the section above. Subjects who sign the informed consent form and are randomized but do not receive the study intervention they are randomized to will be followed in the study as if they have obtained their intervention this deviation from protocol will be documented for post-hoc analysis reasons. Subjects who sign the informed consent form, and are randomized and receive the study intervention, and subsequently withdraw, or are withdrawn or discontinued from the study, maintained in the group to which they are randomized for assessment documentation with notation made as to their withdrawal to assist in the post-hoc analysis.

Study participants who are randomized to the continuous infusion cohort will be provided with information about the pumps themselves and troubleshooting advice. They will also be provided with contact information for the investigators should they run into issues. The troubleshooting of the device will be done as noted in the above section and need for discontinuation of the therapy will be assessed as noted above with safety concerns as the primary reason for discontinuation.

A participant will be considered lost to follow-up if he or she fails to respond to study surveys followed for more than one day of follow up, misses the phone calls, or misses the post-operative office visit planned for postoperative day 10-14 and is unable to be contacted by the study site staff.

The following actions must be taken if a participant fails to respond to study surveys or return to the clinic for a required study visit:

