18. RESEARCH RELATED HARM/INJURY

- *Describe the availability of medical or psychological resources that subjects might need as a result of anticipated problems that may be known to be associated with the research.*
- *If the research is greater than minimal risk, explain any medical treatments that are available if research-related injury occurs, who will provide it, what will be provided, and who will pay for it.*

Adverse events and planned interventions prior to discontinuation

- Failure of catheter placement despite successful administration of single site injection- any participant who was randomized to receive a continuous

pump, but the catheter was unable to be placed will be discontinued from the continuous pump protocol, however these patient's will continue to be followed according to the above stated protocol and their outcomes assessed in an intent-to treat manner based on their initial randomization.

- Continuous Block failure- if patient perceives no benefit from block but pump appears to be functioning patient will be requested to continue the pumps use until the medication dosing is completed, a perceived block failure will be documented.
- Allergy to local anesthetic- if a patient reports a systemic allergic response including but not limited to shortness of breath, diffuse rash, or angioedema the patient will be recommended to discontinue the intervention and seek emergency care. If the patient reports a local confined rash or skin irritation around the catheter site with no systemic symptoms the patient will be recommended to take a dose of Benadryl and apply a warm compress, if symptoms resolve the patient will remain in the study if there is no resolution the patient will be told to discontinue the medication administration and seek care for further evaluation.
- Persistent pain at catheter site- the patient will be advised to place a cold or warm compress at the catheter site and adjust the adhesive bandage if necessary if these interventions do not alleviate the participants pain within 12 hours the patient will be advised to discontinue the intervention.

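### With every analysis by randomised arm, catheter- and infusion-specific harms may be slightly understated; Section 12 should add a supportive safety table by treatment received

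*Combined protocol and SAP*

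**What the plan says.** Section 12 (Intention to Treat) sets one rule for the whole plan: "All analyses will be carried out according to the ITT principle". It defines the set so that "The ITT population will be all subjects randomized, regardless of what treatment they actually received".

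Safety falls under this rule. Among the secondary outcomes in Section 12, "each subject will be categorized as having had one or more adverse events, or not having had any adverse events", and serious adverse events are treated in the same way. For binary outcomes at the follow-up visit, "For each outcome, logistic regression will be used to examine the association between pain control method and that outcome", with site as a covariate. No safety population, analysis by treatment received or catheter-specific denominator is defined.

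The plan expects some patients in the catheter arm to have no catheter. Section 18 describes patients who received the single injection and were randomised to the "pump, but the catheter was unable to be placed will be discontinued from the continuous pump protocol", with "their outcomes assessed in an intent-to treat manner based on their initial randomization". Section 16 says that patients who do not receive their allocated intervention "will be followed in the study as if they have obtained their intervention", and that the deviation is documented for a later post-hoc analysis, which is not described. Section 16 also includes receipt of the allocated treatment in the data collected when the intervention is discontinued.

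**The concern.** Analysis by randomised arm is right for efficacy. For harm, dilution towards no difference is not the cautious direction. Sections 16 and 17 list risks that need a catheter or an infusion, such as migration, catheter-site problems and toxicity during the 48 to 72 hours of home infusion. A patient who never had a catheter cannot contribute such an event but still counts in the denominator. The reported rate then falls below the risk in patients who actually have the device, which is what a clinician or patient would want to know.

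The trial is also open-label. If the grouping of these patients and the coding of failed placement are left to an unspecified post-hoc look, they will be settled by people who have seen the results by arm.

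**Working it through.** **Inputs.** The arm size of 39 comes from the sample size paragraph of Section 12. That figure is a pain calculation and it reproduces: a two-sided two-sample t-test with difference 2, SD 2.5, alpha 0.01 and 80% power needs 38.2, hence 39 per group (power 81.0% at 39). It serves here only as a denominator. The plan states no adverse-event rate, no power for adverse events and no placement-failure rate. Section 16 only calls block failure with a catheter rare. The number unexposed, k, is therefore an assumption: 1, 2, 4 or 6 of 39, so f = k/39 = 2.6%, 5.1%, 10.3% or 15.4%.

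**Step 1, device-specific events.** With risk p_c in exposed patients and p_s in patients with an injection only, the rate reported by randomised arm is (1 − f)p_c + f·p_s. Take p_c = 10%, the top of the 0 to 10% that Section 16 gives for localised inflammation, and p_s = 0 for an event that needs a catheter. The reported rate is 0.10 × (1 − k/39).

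**Step 2, no events seen.** The one-sided 95% upper bound is 1 − 0.05^(1/n). With n = 39 it is 7.4%. With n = 39 − k exposed patients it is higher, as shown.

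| k | Reported rate if the true risk is 10% | Upper bound, n = 39 − k |
|---|---|---|
| 1 | 9.7% | 7.6% |
| 2 | 9.5% | 7.8% |
| 4 | 9.0% | 8.2% |
| 6 | 8.5% | 8.7% |

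**Step 3, events that can also follow a single shot.** The shortfall is f(p_c − p_s), so it shrinks as p_s rises. Local infection is such an event: Sections 16 and 17 list it for the single-shot block too, as a very low risk. At the top of the stated 0 to 3% range for catheters, and with p_s = 0, the reported rate would be 0.03 × 38/39 = 2.9% for k = 1 and 0.03 × 35/39 = 2.7% for k = 4. Any p_s above zero brings it closer to 3%.

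**Step 4, any adverse event (the outcome the plan compares).** Assume, for illustration only, true rates of 20% with a catheter and 10% with a single shot.
- (a) Failed placement is not an adverse event: the difference by arm is (1 − f) × 10 points.
- (b) Failed placement is coded as an adverse event: the catheter-arm rate is (1 − f) × 20% + f, less 10% for the difference.
- (c) As (b), but failed placements are moved to the single-shot group: that group's rate is (3.9 + k)/(39 + k), and the difference is 20% less that rate.

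| k | (a) points | (b) points | (c) points |
|---|---|---|---|
| 1 | 9.7 | 12.1 | 7.8 |
| 2 | 9.5 | 14.1 | 5.6 |
| 4 | 9.0 | 18.2 | 1.6 |
| 6 | 8.5 | 22.3 | −2.0 |

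Against a true difference of 10 points, analysis by arm is too low under (a) and too high under (b). Under (c), a simple two-group split by treatment received understates catheter harm by more than analysis by arm does under (a).

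**The case against.** A safety comparison by randomised arm preserves the randomisation and answers a fair question: what happens to patients for whom a catheter is planned. The absence of a table by treatment received is not an error. With 1 or 2 failures the change is half a percentage point or less, and no conclusion from 39 per arm would turn on it. The plan compares only any AE and any SAE, and specifies no catheter-site rate that could be biased. Section 16 also allows a second placement attempt in recovery and documents non-receipt for later analysis. All of this stands, and it limits the point to an improvement.

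Three stronger readings are tempting, and the documents do not support them.
- A reader might infer that catheter harm is understated as a matter of fact. Section 18 puts failed placement under an adverse-event heading, and the list of adverse events in Section 16 is open-ended. Failures may therefore raise the catheter-arm any-AE rate.
- A reader might infer that infection can occur only with a catheter. Sections 16 and 17 say otherwise.
- A reader might infer that failed placements belong with the single-shot patients. An attempted placement carries its own procedural exposure, and step 4(c) shows that the move can hide catheter harm.

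What the objection does not answer is that the only provision for looking at non-receipt is post hoc and undefined.

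**Conclusion.** The point holds in a limited form. Rates of events that need a catheter or an infusion may be understated by about the fraction of the catheter arm not exposed: 10% would be reported as 9.7% to 8.5% if 1 to 6 of 39 had no catheter. This rests on an assumed number of failures, an event risk of zero without a catheter, and such rates being reported over the randomised arm. For any AE and any SAE the documents do not fix the direction, because they do not say whether failed placement is an adverse event. The efficacy analysis and the sample size of 78 are unaffected. It is a cheap improvement, not a flaw that threatens the trial.

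**What to change.** In Section 12, keep ITT for efficacy and for the randomised AE and SAE comparison, and add:
- A pre-specified supportive safety table by treatment received, with three groups: catheter placed and infusion started; catheter allocated or attempted but not placed, or infusion not started; single shot as allocated.
- Denominators: patients with a catheter placed for catheter-specific events, and patients with an infusion started for pump and infusion events. A patient with a catheter but no infusion counts in the first denominator only.
- A statement of whether failed placement counts as an adverse event, applied in both the randomised comparison and the table.

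The cost is a few sentences and one table. Section 16 already documents non-receipt of the allocated treatment. It would be prudent to confirm that the case report form records catheter placed and infusion started for every patient, not only at discontinuation. The downside is that the table compares groups not formed by randomisation. It must be labelled as such and read as descriptive.

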4. OBJECTIVE(S)/SPECIFIC AIMS AND HYPOTHESES

- *A concise statement of the goal(s) of the current study.*
- *The rationale for and specific objectives of the study.*
- *The goals and the hypothesis to be tested should be stated.*

OBJECTIVES	ENDPOINTS	JUSTIFICATION FOR ENDPOINTS
Primary		
To Compare the efficacy of two different modes of administration of peripheral nerve block for postoperative pain control after primary ACL reconstruction.	Pain control as measured by a visual analogue scale (0-10) on post operative day 1,2,3,4,7, and at first follow up visit (Day 14).	Our study seeks to better clarify the effectiveness of two postoperative pain control methods after ACL reconstruction. Visual analogue scale is commonly used to assess pain in postoperative patients. This is an easy way to assess patients pain in a quick and easy to understand method.
Secondary		
To compare the daily opioid consumption in patients post operatively after ACL Reconstruction.	This will be measured as daily consumption of oxycodone (morphine equivalents) on post operative day 1,2,3,4,7, and 14.	A secondary objective of our study would be to examine pain control objectively by opioid consumption each day. This is a secondary measure of the efficacy of pain control. The hope is that with better pain control via peripheral nerve block patients would be less reliant on opioid pain medication.
To determine the effectiveness of pain control and quality of sleep.	We will measure this by asking if they had a disturbance in their sleep or trouble getting to sleep through email surveys.	Our study wants to look at how pain control and sleep quality are correlated and to analyze if better pain control also allowed patients to have better postoperative sleep habits.

General Well Being	Short Form - 12 Survey given preoperatively and at 14 days post operatively.	This assessment test is to classify changes in general health and wellbeing, physical, and mental health.
Knee Assessment Score	International Knee Documentation Committee Subjective Knee Form (IKDC) to be given preoperatively and at 14 days post operatively.	Designed to assess patients with a variety of knee disorders.

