10. ENDPOINTS

- *Describe the primary and secondary study endpoints*
- *Describe any primary or secondary safety endpoints*

A participant is considered to have completed the study if he or she has completed all phases of the study including the last visit or the last scheduled procedure. The end of the study is defined as completion of the last visit or procedure which we defined as the initial follow up visit in the office and the final survey will be sent out 14 days after the indicated surgery.

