- All patients who are enrolled in this study will have been evaluated and determined to be a candidate for ACL reconstruction surgery. The indications for surgery, determination of need for surgery and physical examination determining this need are independent from the interventions and outcomes being assessed by this study.
- **Efficacy Assessment plan-** All patients will be sent surveys through REDCAP, which is a secure patient secure electronic data capture software on postoperative days 1,2,3,4, 7 and 14. And be assessed in person at the post-operative visit which usually falls between post op day 10-14 depending on weekend and convenience. They will be surveyed for primary and secondary outcomes . Primary outcome will be assessed using visual analog scale 0-10. Secondary outcomes; Opiate consumption, Sleep quality, disturbances in sleep, global health assessment through the SF-12, and knee function through IKDC pre operatively and POD 14. The patient will also be contacted via telephone on post-operative day 1, 2, 3, 4 and 7 to assess for adverse events.
- Screening evaluation will occur during the preoperative visit prior to surgery which generally occurs within 28 days prior to surgery. No separate screening is indicated in this study.
- Procedure for administering study intervention and follow-up procedures. The participant will be seen in the preoperative holding suite prior to surgery to ensure that the patient is still willing to undergo randomization for the study. The patient will then undergo randomization by a computer-based software and the anesthesiologist will be informed of the plan. The participant will undergo anesthesia at the discretion of the anesthesiologist per routine given the participant's clinical baseline. The participant will undergo ACL reconstruction based on the standard of care treatment. Following surgery but prior to leaving the operating room the anesthesiologist will place the adductor canal block and the catheter based on the participant's randomization under ultrasound guidance to ensure proper placement of the block. The participant will then undergo routine

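### Opioid use is primary in Section 12 but secondary in Sections 4 and 11, and no section says which pain score is primary or how many of the three Section 12 outcomes must succeed

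*Combined protocol and SAP*

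**What the plan says.** All places are in the combined protocol and SAP.

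- **Section 4 (objectives table).** The primary endpoint is "Pain control as measured by a visual analogue scale (0-10", at six time points. Opioid use is placed lower: "A secondary objective of our study would be to examine pain control objectively by opioid consumption each day".
- **Section 10 (Endpoints).** No outcome is named. The text defines study completion: "A participant is considered to have completed the study if he or she has completed all phases of the study".
- **Section 11 (Efficacy Assessment plan).** "Primary outcome will be assessed using visual analog scale 0-10". Then: "Secondary outcomes; Opiate consumption, Sleep quality, disturbances in sleep", followed by the SF-12 and IKDC.
- **Section 12 (Primary Outcome).** Three items stand before the Secondary Outcomes heading: maximum pain over 24 hours; current pain ("Current pain will be measured on a scale of 0 to 10"); and "Daily opioid consumption (expressed as morphine equivalents". Seven time points are listed, including day 0.
- **Section 12 (Statistical Methods, Primary Outcomes).** "For each outcome, repeated measures analysis of variance (RMANOVA", with site, day and the method-by-day interaction in the model. Day comparisons follow only if the interaction is significant.
- **Section 12 (Sample Size Justification).** 39 per group, for a 2-point pain difference on a single day, SD 2.5, two-sided 0.01. The 0.01 is justified by six day comparisons.
- **Section 19.** Pain efficacy, opioid use, sleep and satisfaction appear as numbered aims 1 to 4, with no primary or secondary label.

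**The concern.** The sections that classify outcomes disagree about opioid use. Sections 4 and 11 also leave open which of the two Section 12 pain scores is the VAS they mean. Within Section 12 there is no ordering of the three outcomes, no any-or-all rule and no division of alpha between them. Within a single outcome, the plan does not say whether the main effect, the interaction or a day comparison carries the claim, or at what level the first two are tested.

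Suppose opioid use differs and neither pain score does. A report could present this as a primary success by citing Section 12, or as a secondary finding by citing Sections 4 and 11. Neither patients nor physicians are blinded and the outcomes are self-reported, so the trial should not leave that choice open until results are known.

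**Working it through.** **1. The plan's own figure.** Inputs from the Sample Size Justification: difference 2, SD 2.5, two-sided alpha 0.01, power 80%. Standardised difference d = 2/2.5 = 0.8. The normal approximation, n = 2(z₀.₉₉₅ + z₀.₈₀)²/d², gives 37 per group. The noncentral t gives 38.2, so 39, with 81.0% power at 39. The stated size reproduces. It is a calculation for one pain score on one day; no opioid difference or SD is given.

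**2. What the 0.01 covers.** Six days at 0.01 sum to 6 × 0.01 = 0.06 within one outcome. Across three outcomes the sum is 18 × 0.01 = 0.18. These are upper bounds that ignore the interaction gate. They show only that the adjustment was set for days, not outcomes.

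**3. False-positive chance by success rule.** Assumptions not in the documents: no true difference on any outcome, each main effect tested once at two-sided 0.05, and pairwise correlation r between the three test statistics.

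- One primary outcome: 5%.
- Any one of three, r = 0: 1 − 0.95³ = 14.3%.
- Any one or all of three, by simulation of a trivariate normal (2 million draws):

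| r | any of three | all three |
|---|---|---|
| 0 | 14.3% | 0.01% |
| 0.3 | 13.6% | 0.09% |
| 0.5 | 12.5% | 0.3% |
| 0.7 | 10.9% | 0.9% |
| 0.9 | 8.4% | 2.3% |

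The last column applies only when all three outcomes are null. In general, the chance that all three are significant cannot exceed the chance that a null one is, so the ceiling is 5%. It is nearly reached when the other two truly differ.

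If the deciding test were instead a day comparison at 0.01 after an interaction at 0.05, simulation (39 per group, compound symmetry, within-patient correlation 0.3-0.7) gives 0.6-1.8% for one outcome and 1.3-5.0% for any of three.

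**4. Why the deciding test must also be stated.** Take six days and compound symmetry with within-patient correlation ρ. The SD of a patient's six-day mean is 2.5 × √[(1 + 5ρ)/6], which is 1.61 at ρ = 0.3 and 2.17 at ρ = 0.7. Section 16 says the catheter stays in for 48-72 hours, so consider a 2-point benefit on days 1-3 only. The mean difference is 2 × 3/6 = 1 point, and main-effect power at 0.05 with 39 per group is 52-77%. The gated day route has 94-97%. If the 2 points hold on all six days, the figures are 98-100% and about 5%, because a constant difference creates no interaction. The two routes can therefore reach opposite conclusions.

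**The case against.** The best defence is that the intention is clear. Every section that classifies outcomes calls pain primary, the trial is sized on pain, and Section 19 puts pain first and opioid use second. On this view the opioid item in Section 12 is a misplaced bullet. Much of this stands: pain as the primary domain is not in doubt, and it would be wrong to infer that the trial has no primary objective.

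It does not settle the point. The secondary methods in Section 12 cover only binary outcomes and satisfaction, so the primary RMANOVA is the only analysis given for opioid use; moving the bullet alone would leave it with none. The methods paragraph is written for several primary outcomes. The sample size borrows pain with movement from a shoulder study, which does not identify maximum or current pain. Numbered aims are not a testing order.

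Three stronger readings are tempting and are not supported:

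- *The type I error is inflated.* That needs an any-one-wins rule, which the plan never states. Other readings keep the error at or below 5%.
- *Section 12 makes an opioid-only result a primary success.* It permits that claim; without a success rule it does not establish it.
- *Requiring all three would hold the error near 2%.* That is true only if all three outcomes are null.

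The figures also have limits. The plan mentions a nominal 5% level but does not assign it to the main effect or interaction. The simulations treat outcomes as normal, which may fit opioid use poorly; the plan itself allows a transformation or non-parametric method.

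**Conclusion.** The contradiction is real and nothing in the documents resolves it. Three things are unsettled: the status of opioid use, which pain score is primary, and whether one or all of the Section 12 outcomes must be significant. With main effects at an assumed 0.05 and no true differences, the false-positive chance of the primary claim is about 8-14% if any of three may win (correlation 0.9 down to 0) and 5% with a single primary; if all three are required it is at most 5%. The defect is that the plan does not say which of these applies, so its error rate is undefined. The sample size arithmetic is sound for the single-day pain test it describes.

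**What to change.** 1. Name one pain measure, maximum or current (the sponsor's choice), as the single primary outcome. Use one day set: Section 4 and the sample size use six time points, Section 12 uses seven. State this identically in Sections 4, 10, 11 and 12, before any look at the data.
2. Make the other pain measure and daily opioid consumption secondary, and state that the same RMANOVA applies to them. If opioid use is to remain confirmatory, test it in fixed sequence, only after the primary pain claim is met.
3. State which test on the primary outcome decides (main effect, interaction or day comparison) and at what level. Keep it consistent with the single-day 0.01 basis of the sample size, or restate the power for the test chosen.

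**Cost.** A protocol amendment. A result on opioid use or the other pain measure alone could no longer be called a primary success. No extra patients are needed if the single-day test decides: 39 per group gives 81.0%, a figure that does not allow for the interaction gate. By comparison, keeping all three as primary and splitting the single-day 0.01 equally (0.01/3 = 0.0033 each) would need 47 per group (94 in total) for the pain difference; 39 per group would then give 69.0% power.
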